**Table 5.2.1-1: PFS Hazard Rates and Hazard Ratios (Nivolumab plus Chemotherapy vs. Chemotherapy)**

Periods	Hazard Rates for Chemotherapy	Hazard Ratios (3 months delay)	Hazard Ratios (6 months delay)
0-3 months	0.09	1	1
3-6 months	0.17	0.56	1
6-10 months	0.2	0.56	0.56
> 10 months	0.13	0.56	0.56

**Table 5.2.1-2: Summary of Sample Size Parameters and Schedule of Analyses for PFS (Nivolumab plus Chemotherapy vs. Chemotherapy)**

	3 months Delay	6 months Delay
# subjects with PD-L1 CPS $\geq 5^a$	554	554
Hypothesized delayed period	3	6
Hypothesized HR after delayed period	0.56	0.56
Hypothesized median in control arm	5.5 months	5.5 months
Significance level (2-sided)	0.02	0.02
Enrollment Period (from start of 1:1:1)	25.4 months	25.4 months
Minimum follow-up / Expected number of events a,b,c	12 months / 497	12 months / 506
Time of Analysis	37.4 months	37.4 months
power b	99%	66%
average HR b	0.66	0.80

a Based on 35% prevalence of PD-L1 CPS  $\geq 5$

b Results based on simulations.

c Number of events for the nivolumab plus chemotherapy vs. chemotherapy comparison in total.

**Overall Survival**

A delayed separation of at least 6 months between the OS distribution of pembrolizumab + chemotherapy and chemotherapy was observed. To fully capture the treatment effect, the interim and final analyses of OS will be conducted after a minimum follow up after the last patient randomized.

The interim analysis will be conducted after at least 12 months minimum follow-up, and the final analysis will be conducted after at least 24 months minimum follow-up.

With 24 months minimum follow-up at final analysis it is expected that 466 events will be observed. With an average HR of 0.74 modelled as a 2-piece hazard ratio, a delayed effect with a HR of 1 versus chemotherapy for the first 6 months followed by a constant HR of 0.65 (see Table 5.2.1-3 ) the power will be approximately 85% with a Type I error of 3% (two-sided) (see Table 5.2.1-4).

For the OS interim and final analyses, all the events reported in the database at time of database locks will be used for the primary analyses.

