**5.2.1 Sample Size: Nivolumab plus Chemotherapy vs. Chemotherapy**

**Progression Free Survival**

Concurrently randomized subjects to nivo+chemo and chemo arms with PD-L1 CPS  $\geq 5$  will be used for the PFS analysis. Given the delayed separation in the PFS distributions between pembrolizumab + chemotherapy and chemotherapy, the PFS analysis will be conducted after a minimum of 12 months follow-up after the last patient is randomized.

As such, the PFS analysis will be conducted after the following criteria are all met:

- CPS scoring by central laboratories is complete
- a minimum follow-up of 12 months

The HR is modelled as a 2-piece hazard ratio with a delayed effect of 3 and 6 months (a HR of 1 versus chemotherapy for the first 3 or 6 months) followed by a constant HR of 0.56 (see Table 5.2.1-1). With 12 months minimum follow-up it is expected that the number of events will range between 497 and 506 respectively and the power will range between approximately 99% and 60% with a Type I error of 2% (two-sided) (see Table 5.2.1-2).

The primary PFS analysis will be based on all the events observed at time of database lock.

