**Table 5.2.1-3: Assumed OS Hazard Rates and Hazard Ratios (Nivolumab plus Chemotherapy vs. Chemotherapy)**

Periods	Hazard Rates for Chemotherapy	Hazard Ratio
0-3 months	0.036	1
3-6 months	0.06	1
6-24 months	0.08	0.65
>24 months	0.05	0.65

**Table 5.2.1-4: Summary of Sample Size Parameters and Schedule of Analyses for OS (Nivolumab plus Chemotherapy vs. Chemotherapy)**

# with PD-L1 CPS $\geq 5^a$	554
Hypothesized delayed period	6 months
Hypothesized HR after delayed period	0.65
Hypothesized median in control arm	11.1 months
Significance level (2-sided)	0.03
Enrollment Period (from start of 1:1:1)	25.4 months
INTERIM ANALYSIS #1 for OS	
Minimum follow-up/Expected number of events a,b,c	12 months/395
Time of analysis d	37.4 months

**Table 5.2.1-4: Summary of Sample Size Parameters and Schedule of Analyses for OS (Nivolumab plus Chemotherapy vs. Chemotherapy)**

Significance level c	0.0164
Power	64%
FINAL ANALYSIS	
Minimum follow-up/Expected number of events a,b,c	24 months/466
Time of analysis d	49.4 months
Significance level	0.0252
Power b	85%
Average HR	0.74

a Based on a 35% prevalence of PD-L1 CPS  $\geq 5$ .

b Results based on simulations

c Number of events for the nivolumab plus chemotherapy vs. chemotherapy comparison in total.

d After first patient randomized to nivolumab + chemotherapy or chemotherapy in 1:1:1 randomization.

e Significance levels will be calculated based on the actual number of deaths at each interim analysis

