### **5.2.2 Power Considerations for Nivolumab plus Ipilimumab vs. Chemotherapy**

OS between nivolumab+ipilimumab vs chemotherapy will be tested as a secondary objective. This comparison will be tested if at least one primary endpoint (PFS or OS of nivolumab + chemotherapy vs. chemotherapy in PD-L1 CPS  $\geq 5$  subjects) meets statistical significance. The nivolumab+ipilimumab vs. chemotherapy OS comparison will be conducted at the planned final comparison of OS for nivolumab+chemotherapy vs. chemotherapy. This corresponds to approximately 36 months of minimum follow-up for the nivolumab + ipilimumab and chemotherapy arm.

With approximately 36 months minimum follow-up at final analysis it is expected that 240 events will be observed. With an average HR of 0.7 modelled as a 4-piece hazard ratio (see [Table 5.2.2-](#)

1) the power will range between 63% and 73% for Type I error of 1.5% and 3.5% (two-sided) (see Table 5.2.2-2).

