#### **7.5.2.4 Analysis of Overall Survival**

OS in randomized CPS  $\geq 5$  subjects will be compared between nivo+chemo vs. chemo at the interim and final analyses, using stratified log-rank test, stratified by the stratification factors as specified in [Table 7.5-1](#). An O'Brien and Fleming  $\alpha$ -spending function will be employed to determine the nominal significance levels for the interim and final analyses (see [Table 7.5.1-1](#)). The stratified hazard ratio between the treatment groups will be presented along with 100\* (1 -  $\alpha$ )% CI (adjusted for interim) and will be calculated using a stratified Cox proportional hazards model, with treatment as the sole indicator covariate (for the nivo+chemo and chemo arm). Ties will be handled using the exact method.

OS will be estimated using the KM techniques. A two-sided 95% CI for median OS in each treatment group will be computed via the log-log transformation method. OS rates at fixed time points (eg, 12, 18, 24, 36 months, depending on the minimum follow-up) will be presented along with their associated 95% CIs. These estimates will be derived from the Kaplan Meier estimate and, corresponding CIs will be derived based on Greenwood formula for variance derivation and on log-log transformation applied on the survivor function.

The status of subjects who are censored in the OS KM analysis will be tabulated for each treatment group using the following categories:

- On-study (on-treatment, in follow-up)
- Off-study (lost to follow-up, withdraw consent, never treated)

A by-subject listing will be presented including treatment group, first and last dose date, whether the subject died, and if censored, the reason, event/censored date and OS duration.

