### Update of Power Calculation for PFS and OS

As indicated in [section 8.1.2](#) of the protocol, “the power statement of the primary endpoints of PFS and OS will be updated using the actual prevalence and documented in the final SAP prior to first database lock for efficacy analysis.” Based on the observed prevalence of PD-L1 CPS  $\geq 5$  of 60% among all randomized subjects, [Table 5.2.1-2](#) and [Table 5.2.1-4](#) are therefore updated with [Table 1](#) and [Table 2](#). Specifically, the number of subjects with PD-L1 CPS  $\geq 5$ , the expected number of events at interim and final, and the power at interim and final were updated and are highlighted in the tables.

Similarly for the nivolumab+ipilimumab comparisons, based on the observed prevalence of PD-L1 CPS  $\geq 5$  of 60% among all randomized subjects and  $\alpha=0.035$  hierarchically passed from the

primary nivolumab+chemotherapy versus chemotherapy results at the primary database lock on 10Jul2020, [Table 5.2.1-2](#) is therefore updated with [Table 3](#).

**Table 1 Updated Summary of Sample Size Parameters and Schedule of Analyses for PFS (Nivolumab + Chemotherapy vs. Chemotherapy)**

	3 months Delay	6 months Delay
# subjects with PD-L1 CPS $\geq 5^a$	949	949
Hypothesized delayed period	3	6
Hypothesized HR after delayed period	0.56	0.56
Hypothesized median in control arm	5.5 months	5.5 months
Significance level (2-sided)	0.02	0.02
Enrollment Period (from start of 1:1:1)	25.4 months	25.4 months
Minimum follow-up / Expected number of events a,b,c	12 months /841	12 months /857
Time of Analysis	37.4 months	37.4 months
power b	99.9%	84.0%
average HR b	0.66	0.80

a Based on 60% prevalence of PD-L1 CPS  $\geq 5$

b Results based on simulations.

c Number of events for the nivolumab plus chemotherapy vs. chemotherapy comparison in total.

**Table 2 Updated Summary of Sample Size Parameters and Schedule of Analyses for OS (Nivolumab + Chemotherapy vs. Chemotherapy)**

# with PD-L1 CPS $\geq 5^a$	949
Hypothesized delayed period	6 months
Hypothesized HR after delayed period	0.65
Hypothesized median in control arm	11.1 months
Significance level (2-sided)	0.03
Enrollment Period (from start of 1:1:1)	25.4 months
INTERIM ANALYSIS #1 for OS	
Minimum follow-up/Expected number of events a,b,c	12 months/680
Time of analysis d	37.4 months

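### Several stated powers match an unstratified log-rank test, but the formal tests are stratified over 24 or 12 cells and give less power if those cells are not prognostic

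*SAP*

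**What the plan says.** The power statements are in SAP 5.2.1 and 5.2.2, repeated from Protocol 8.1.4 and 8.1.5, with an update in SAP Appendix 5. N+C is nivolumab plus chemotherapy, N+I nivolumab plus ipilimumab, each against chemotherapy in subjects with CPS ≥ 5.

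- OS, N+C: "the power will be approximately 85% with a Type I error of 3% (two-sided", under a hazard ratio of 1 "for the first 6 months followed by a constant HR of 0.65". "With 24 months minimum follow-up at final analysis it is expected that 466 events will be observed".
- PFS, N+C: "the power will range between approximately 99% and 60% with a Type I error of 2% (two-sided", for a 3- or 6-month delay.
- OS, N+I: "the power will range between 63% and 73% for Type I error of 1.5% and 3.5% (two-sided".
- Appendix 5, after CPS scoring gave 60% prevalence: "the expected number of events at interim and final, and the power at interim and final were updated". It gives 949 subjects for N+C (OS 87.3% interim and 97.9% overall; PFS 99.9% and 84.0%) and 489 for N+I (93%).

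SAP 5.2 says only that the figures come from EAST simulations. Neither document says whether the simulated test was stratified, and neither gives cell counts or stratum effects.

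The formal OS test is specified in SAP 7.5.2.4 as a comparison "using stratified log-rank test, stratified by the stratification factors as specified in" Table 7.5-1. Sections 7.5.2.1 (PFS) and 7.5.3.1 (N+I OS) do the same. The table lists region, ECOG and TPS, plus regimen for N+C. The unstratified log-rank appears only as a supportive analysis.

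**The concern.** A stratified log-rank compares arms only within a cell. When one arm of a cell has no one left at risk, later events in that cell carry no information. With about 23 subjects per cell this happens in the tail, and the tail is where the plan places all its benefit: after 3 or 6 months for N+C, and mainly after 6 months for N+I, which also assumes early harm (hazard ratio 2.75 in months 0–3).

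If power was simulated for one pooled comparison, the stated figures describe a more powerful test than the one that decides the trial. Protocol 8.1.2 commits the sponsor to updating the power statement with the actual prevalence. That update should describe the test in use.

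**Working it through.** **Inputs.** Hazards and effects are from SAP Table 5.2.1-1 (PFS), Table 5.2.1-3 ("Assumed OS Hazard Rates and Hazard Ratios (Nivolumab plus Chemotherapy vs. Chemotherapy") and Table 5.2.2-1 (N+I). Accrual is from SAP 5.1. For N+C, 1098 × 2/3 = 732 subjects over 14.3 months (27-Mar-2017 to 05-Jun-2018), then 850 over 25.4 − 14.3 = 11.1 months, total 1582. For N+I, 83 over 4.4 months, then 732 over 14.3, total 815. Sizes are 0.35 × 1582 = 554, 0.60 × 1582 = 949, 0.35 × 815 = 285 and 0.60 × 815 = 489. Analyses are at 37.4 and 49.4 months (N+C) and 54.4 months (N+I). OS levels are 0.0164 and 0.0252; PFS 0.02; N+I 0.015 or 0.035. No dropout, since none is stated.

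**Cells.** N+C: 3 × 2 × 2 × 2 = 24. N+I: 3 × 2 × 2 = 12. The ORR formulas in SAP 7.5.2.9 and 7.5.3.8 sum over the same numbers. Subjects per cell: 554/24 = 23, 285/12 = 24, 949/24 = 40, 489/12 = 41.

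**Model check.** Control OS: 3 × 0.036 + 3 × 0.06 = 0.288 at 6 months, so the median is 6 + (0.693 − 0.288)/0.08 = 11.1 months, as stated. Control PFS: 3 + (0.693 − 0.27)/0.17 = 5.5 months, as stated.

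**Closed-form check of the 85%.** Φ(½√466 × |ln 0.74| − z) at two-sided 0.0252 is Φ(10.79 × 0.301 − 2.24) = 84.4%. This formula takes no account of strata.

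**Simulation.** The main runs used 10,000 to 20,000 trials; shorter runs varied the assumed cell sizes from equal to very uneven. Simulated events at 554 and 285 subjects were 398 and 466 for OS (stated 395 and 466), 496 and 504 for PFS (497 and 506) and 242 for N+I (240). The last column assumes cells with no prognostic effect and spans all runs.

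| Power | Stated | Unstratified | Stratified |
|---|---|---|---|
| OS interim, 554 | 64% | 64.4–64.7% | 55–59% |
| OS overall, 554 | 85% | 84.8–84.9% | 78–80% |
| PFS 6-month delay, 554 | 60% | 59.4% | 43–48% |
| PFS 3-month delay, 554 | 99% | 99.0% | 97–98% |
| N+I, 285, α 0.015 | 63% | 62.8–63.1% | 49–54% |
| N+I, 285, α 0.035 | 73% | 74.3–75.0% | 63–66% |
| OS interim, 949 | 87.3% | 89.0–89.6% | 85–87% |
| OS overall, 949 | 97.9% | 97.7–98.0% | 96–97% |
| PFS 6-month delay, 949 | 84.0% | 85.2% | 76–80% |
| PFS 3-month delay, 949 | 99.9% | 100% | 99.9–100% |
| N+I, 489, α 0.035 | 93% | 93.6–93.8% | 90–91% |

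**Why PFS with 6-month delay loses most.** At 554 there are 554/48 = 11.5 subjects per arm per cell. When the PFS effect starts at 6 months, exp(−(0.27 + 0.51)) = 46% are event-free, about 5 per arm per cell. When the OS effect starts, exp(−0.288) = 75% are alive, about 9.

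**Prognostic cells.** Here the documented population curves are held fixed, cells are uneven, and the spread of log-hazards between cells (SD) is varied. Stratified power:

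| | SD 0.2 | SD 0.35 | SD 0.5 | SD 0.7 |
|---|---|---|---|---|
| OS overall, 554 | 81.0% | 83.3% | 88.1% | 91.8% |
| PFS 6-month delay, 554 | 48.2% | 49.8% | 53.6% | 57.6% |
| N+I, 285, α 0.015 | 53.5% | 56.2% | 60.0% | 68.5% |
| OS overall, 949 | 97.0% | 98.4% | 99.0% | 99.5% |
| PFS 6-month delay, 949 | 77.5% | 80.9% | 85.2% | 88.6% |
| N+I, 489, α 0.035 | 91.6% | 92.7% | 94.9% | 96.9% |

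**The case against.** The strongest reply has three parts.

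First, the factors were chosen because they are prognostic. Protocol 1.1.10 cites performance status as a predictor of survival, and Protocol 1.1.1 gives median OS of 12–14 months in Asia against 8–11 in the US and Europe. With the stated curves held, an SD of 0.35 brings OS at 554 back to 83.3%, and 0.5 takes it above the unstratified value. This stands, and it is why the loss cannot be given as one number. It does not settle the matter. PFS with 6-month delay at 554 stays below 60% at every spread tried. Applying the stated hazard ratio within cells and multiplying the stated hazards by cell effects lowers power instead: OS at 554 falls to 73–80% for SD 0.3–0.5. Much of that fall comes from the changed population curves rather than from stratification, since the unstratified test falls too.

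Second, Appendix 5 supersedes the planning sizes, and at 949 and 489 most losses are small. This stands.

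Third, SAP version 5.0 postdates the N+C PFS and interim OS analyses, enrollment is closed and timing is by calendar, so these powers set no sample size. This lowers the urgency. The N+I test is still to be run under this SAP.

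A reader might infer that every stated power is an unstratified figure. The documents do not support that: 99%, 99.9% and 97.9% are within about 2 points under both tests, and 87.3% lies between them. The 66% for the 6-month delay in SAP Table 5.2.1-2 fits neither and conflicts with the 60% in the SAP text and protocol; that is a separate error. A reader might also infer that N+I strata should be pooled. That would change a prespecified test after the N+C report, which shares chemotherapy subjects with the N+I comparison.

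**Conclusion.** The point holds in limited form. Under the plan's model of one hazard curve per arm, seven stated powers (64%, 85%, 60%, 63%, 73%, 84.0% and 93%) fit an unstratified test. That this test was the one simulated is inferred from the match; neither document says so.

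With non-prognostic cells, stratification costs about 5–7 points for OS overall, 11–17 for PFS with 6-month delay and 9–14 for N+I at 554 and 285 subjects. At 949 and 489 it costs about 1 point for final OS, 3–4 for N+I and 5–10 for PFS with 6-month delay. These figures rest on assumed cell sizes, no dropout and no prognostic effect. With prognostic strata and the stated curves held, the loss shrinks and can become a gain, most readily for OS.

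This is a correction to the power statement. It is not evidence that the trial is underpowered at its actual size, and it does not touch the validity of the stratified test or its Type I error.

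**What to change.** State in SAP 5.2 and Appendix 5 which log-rank test was simulated. Re-run the simulation with the stratified test as specified, using blinded, pooled IRT cell counts among subjects with CPS ≥ 5. Restate the affected powers in SAP 5.2.1, 5.2.2 and Appendix 5 Tables 1–3, with a sensitivity range for prognostic strata that says whether the stated hazards are held as population curves or applied within cells. Correct the 66% in Table 5.2.1-2 separately.

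The cost is one simulation run and some SAP wording. Some stated powers will probably fall. Tests, strata, alpha, sample size and timing do not change.

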**Table 5.2.1-3: Assumed OS Hazard Rates and Hazard Ratios (Nivolumab plus Chemotherapy vs. Chemotherapy)**

Periods	Hazard Rates for Chemotherapy	Hazard Ratio
0-3 months	0.036	1
3-6 months	0.06	1
6-24 months	0.08	0.65
>24 months	0.05	0.65

**Table 5.2.1-4: Summary of Sample Size Parameters and Schedule of Analyses for OS (Nivolumab plus Chemotherapy vs. Chemotherapy)**

# with PD-L1 CPS $\geq 5^a$	554
Hypothesized delayed period	6 months
Hypothesized HR after delayed period	0.65
Hypothesized median in control arm	11.1 months
Significance level (2-sided)	0.03
Enrollment Period (from start of 1:1:1)	25.4 months
INTERIM ANALYSIS #1 for OS	
Minimum follow-up/Expected number of events a,b,c	12 months/395
Time of analysis d	37.4 months

**Table 5.2.1-4: Summary of Sample Size Parameters and Schedule of Analyses for OS (Nivolumab plus Chemotherapy vs. Chemotherapy)**

Significance level c	0.0164
Power	64%
FINAL ANALYSIS	
Minimum follow-up/Expected number of events a,b,c	24 months/466
Time of analysis d	49.4 months
Significance level	0.0252
Power b	85%
Average HR	0.74

a Based on a 35% prevalence of PD-L1 CPS  $\geq 5$ .

b Results based on simulations

c Number of events for the nivolumab plus chemotherapy vs. chemotherapy comparison in total.

d After first patient randomized to nivolumab + chemotherapy or chemotherapy in 1:1:1 randomization.

e Significance levels will be calculated based on the actual number of deaths at each interim analysis

With an assumed PD-L1 CPS  $\geq 5$  prevalence of 35% and under the following piecewise HR (HR of 1 vs. chemotherapy for the first 6 months followed by a constant HR of 0.65) the target number of OS events at interim and final analyses is estimated to be 395 and 466 respectively. Using the Lan-DeMets  $\alpha$  spending function with O'Brien and Fleming type of boundary, the significance levels for OS at interim and final analyses are 0.0164 and 0.0252 respectively. At time of interim analysis, the significance level will be adjusted according to actual events observed at OS interim and using the estimated final number of events. At final analysis the significance level will be calculated using the number of events in the database at time of database lock and considering the  $\alpha$ -level already spent at interim analysis as well as the actual correlation among the test statistics.

### **5.2.2 Power Considerations for Nivolumab plus Ipilimumab vs. Chemotherapy**

OS between nivolumab+ipilimumab vs chemotherapy will be tested as a secondary objective. This comparison will be tested if at least one primary endpoint (PFS or OS of nivolumab + chemotherapy vs. chemotherapy in PD-L1 CPS  $\geq 5$  subjects) meets statistical significance. The nivolumab+ipilimumab vs. chemotherapy OS comparison will be conducted at the planned final comparison of OS for nivolumab+chemotherapy vs. chemotherapy. This corresponds to approximately 36 months of minimum follow-up for the nivolumab + ipilimumab and chemotherapy arm.

With approximately 36 months minimum follow-up at final analysis it is expected that 240 events will be observed. With an average HR of 0.7 modelled as a 4-piece hazard ratio (see [Table 5.2.2-](#)

1) the power will range between 63% and 73% for Type I error of 1.5% and 3.5% (two-sided) (see Table 5.2.2-2).

**Table 5.2.2-1: Assumed OS Hazard Rates and Hazard Ratios (Nivolumab plus Ipilimumab vs. Chemotherapy)**

Periods	Hazard Rates for Chemotherapy	Hazard Rates for Nivo + Ipilimumab	Hazard Ratio
0-3 months	0.036	0.099	2.75
3-6 months	0.06	0.054	0.9
6-24 months	0.08	0.0328	0.41
>24 months	0.05	0.0205	0.41

**Table 5.2.2-2: Summary of Sample Size Parameters and Schedule of Analyses for OS (Nivolumab plus Ipilimumab vs. Chemotherapy)**

	Alpha =0.015	Alpha=0.035
# with PD-L1 CPS $\geq 5^a$	285	285
Hypothesized distribution	See Table 5.2.2-1	See Table 5.2.2-1
Hypothesized median in control arm	11.1 months	11.1 months
Significance level (two-sided)	0.015	0.035
Enrollment Period (from start of 1:1)	18.7 months	18.7 months
Time of analysis /Expected number of events a,b,c	54.4/240	54.4/240
Power b	63%	73%
Average HR b	0.70	0.70

a Based on 35% prevalence of PD-L1 CPS  $\geq 5$

b Results based on simulations.

c Number of events for the nivolumab plus ipilimumab vs. chemotherapy comparison in total.

## 6 STUDY PERIODS, TREATMENT REGIMENS AND POPULATIONS FOR ANALYSES

### 6.1 Study Periods

- Baseline period:
  - Baseline evaluations or events will be defined as evaluations or events that occur before the date and time of the first dose of study treatment. Evaluations (laboratory tests, and vital signs) on the same date and time of the first dose of study treatment will be considered as baseline evaluations. Events (AEs) on the same date and time of the first dose of study treatment will not be considered as pre-treatment events.

- In cases where the time (onset time of event or evaluation time and dosing time) is missing or not collected, the following definitions will apply:
  - ◆ Pre-treatment AEs will be defined as AEs with an onset date prior to but not including the day of the first dose of study treatment;
  - ◆ Baseline evaluations (laboratory tests and vital signs) will be defined as evaluations with a date on or prior to the day of first dose of study treatment.
- If there are multiple valid assessments on or prior to the first dose of study treatment:
  - ◆ For PD-L1, among the records prior to or on first dose date (and time if collected), identify first those with quantifiable test result. If there are no records with quantifiable test result, then select those with indeterminate result (“INDETERMINATE”). If there are no records with indeterminate test result, then select those with unavailable result (“NOT EVALUABLE”). If there are no records with unavailable test result, then select those with not reported or not available result (all other records). The latest record will be used as the baseline in the analyses. If there is more than one record for the latest date, then choose the one with the greatest specimen ID. This derivation will apply to tumor positive score (TPS) and composite positive score (CPS)
  - ◆ For Anti-Drug Antibody (ADA), the record related to the most recent assessment among those records where date (and time if collected) of nivolumab or ipilimumab immunoglobulin (IMG) assessment is less than or equal to the date (and time if collected) of the first nivolumab or ipilimumab dose date respectively.
- Post baseline period:
  - On-treatment AEs will be defined as AEs with an onset date and time on or after the date and time of the first dose of study treatment (or with an onset date on or after the day of first dose of study treatment if time is not collected or is missing). For subjects who are off study treatment, AEs will be included if event occurred within a safety window of 30 days (or 100 days depending on the analysis) after the last dose of study treatment. No “subtracting rule” will be applied when an AE occurs both pre-treatment and post-treatment with the same preferred term and grade.
  - On-treatment evaluations (laboratory tests and vital signs) will be defined as evaluations taken after the day (and time, if collected and not missing) of first dose of study treatment. For subjects who are off study treatment, evaluations should be within a safety window of 30 days (or 100 days depending on the analysis) after the last dose of study treatment.

Late-emergent drug-related AEs will be defined as drug-related AEs with an onset date greater than 100 days after the last dose of study treatment in subjects who are off study treatment.

